## PROTOCOL SYNOPSIS

TITLE	A phase II, single-site, double-blind, placebo-controlled randomized withdrawal study assessing the efficacy and safety of sarilumab in patients with glucocorticoid-dependent sarcoidosis
STUDY PHASE	Phase IIb
INDICATION	Glucocorticoid-dependent sarcoidosis
INVESTIGATIONAL PRODUCT OR PROCEDURE	Sarilumab
PRIMARY OBJECTIVE(S)	To demonstrate that sarilumab treatment is effective for inducing and maintaining glucocorticoid-free remission in male or female patients aged 18 to 75 with biopsy proven, active, glucocorticoid-dependent sarcoidosis
SECONDARY OBJECTIVE(S)	To determine the number of patients in glucocorticoid-free remission and the change in prednisone dose compared to baseline at Week 16, after the open-label period (Period 1) of the study. Additional secondary objectives at both Week 16 and Week 28 are to demonstrate that sarilumab treatment is effective for reducing disease manifestation-specific metrics, for improving laboratory parameters, and for reducing cumulative prednisone dose. An important secondary objective is to demonstrate safety in this patient population.
TREATMENT SUMMARY	During Period 1 of this study, fifteen patients will receive sarilumab 200mg subcutaneously every two weeks in an open-label fashion. Subjects will continue their background disease modifying anti-rheumatic drug (DMARD) therapies and current glucocorticoid dose (prednisone $\geq$ 10 mg and $\leq$ 60 mg daily or alternate glucocorticoid equivalent is required for study entry). During the screening period, all patients will change their glucocorticoid to prednisone with stable dosing for at least 14 days before their baseline visit. If a patient is on a prednisone dose between 40 mg daily and 60 mg daily, the dose will be

	
reduced to 40 mg daily by the end of week 3 at the clinician's discretion. Starting at week 4, all patients will begin a scheduled prednisone taper that will take place from week 4 until week 16.
 
Patients will be required to adhere to this tapering protocol. If a violation in the tapering schedule occurs, the patient will be deemed a nonresponder. Patients will be required to fill out a daily steroid diary to clearly document their daily prednisone intake. All attempts will be made to perform a pill count at each visit.
 
During Period 2 of the study (starting at Week 16), the patients that responded in Period 1 will be randomized to withdraw from sarilumab. Patients will be assigned in a blinded, 1:1 fashion to receive either sarilumab 200mg subcutaneously every two weeks or matching placebo.

SAMPLE SIZE	15 patients
STATISTICAL CONSIDERATIONS	
The sample size for Period 1 of the trial of 15 patients was calculated based on the assumption that 80% of the patients will respond to open-label sarilumab, allowing for 12 patients to enroll in the randomized withdrawal Period 2 of the study. The sample size of 12 for Period 2 was calculated based on the assumption that 85% of the placebo group (roughly 5 out of 6) will flare (i.e., require reinitiation of prednisone) over the subsequent 12 weeks compared to 15% (roughly 1 out of 6) in the sarilumab group. This relative hazard of 0.20 gives a power of 80% with an alpha of 0.05 to detect a difference between treatment groups assuming Kaplan-Meier analysis.
 
A sample size of 15 was deemed recruitable at Stanford after searching the Stanford medicine Research data Repository (STARR), which is a clinical data warehouse containing all patients seen at Stanford Hospital and Clinics. A search for patients

between the ages of 18 and 75 who were given the diagnosis code for sarcoidosis on at least two separate occasions within the last year and who are currently on prednisone, yields 200 potential patients. Assuming half of these are coded correctly, and one-third of those truly have glucocorticoid-dependent, refractory disease, that leaves roughly 30 patients to screen, half of which we anticipate will be eligible for, and willing to participate in, the study. Our IRB will allow us to identify specific patients within STARR whom we can contact to determine their interest in the study.

## SCHEMA

## LIST OF ABBREVIATIONS AND DEFINITION OF TERMS

ACE	Angiotensin converting enzyme
ADL	Activities of daily living
AE	Adverse event
ALT	Alanine aminotransferase
ANA	Anti-nuclear autoantibody
ANC	Absolute neutrophil count
AST	Aspartate aminotransferase
BSA	Body surface area
CBC	Complete blood count
CIB	Clinical investigation brochure
CK	Creatinine kinase
CNS	Central nervous system
CRF	Case report/Record form
CR	Complete response
DMARDs	Disease modifying anti-rheumatic drugs
DLT	Dose Limiting Toxicity
DSMB	Data Safety Monitoring Board
ECG	Electrocardiogram
FACIT	Functional assessment of chronic illness therapy
GI	Gastrointestinal
Hgb	Hemoglobin
HIV	Human Immunodeficiency Virus
IL-6	Interleukin-6
IL-6-R	Interleukin-6 receptor
IP	Investigational product
IRB	Institutional Review Board
IUD	Intrauterine device
IV	Intravenous
LDH	Lactate dehydrogenase
LLN	Lower limit of normal
NSAIDs	Non-steroidal anti-inflammatory drugs
OS	Overall survival
PFTs	Pulmonary function tests
PK	Pharmacokinetic
PLT	Platelet
PR	Partial response
QD	Once daily
RBC	Red blood cells
RF	Rheumatoid factor
RR	Response rate
SAE	Serious adverse event
SD	Standard deviation
SEM	Standard error of the mean

SJC	Swollen joints count
TB	Tuberculosis
TEAEs	Treatment emergent adverse events
TJC	Tender joints count
TTP	Time to progression
ULN	Upper limit of normal
UNK	Unknown
VAS	Visual analog scale
WBC	White blood cell
WHO	World Health Organization

## 1. OBJECTIVES

### 1.1. Primary Objective

The primary objective of this study is to determine if sarilumab treatment is effective for inducing and maintaining glucocorticoid-free remission in male or female patients aged 18 to 75 with biopsy proven, active, glucocorticoid-dependent sarcoidosis affecting any organ other than the heart or the central nervous system.

### 1.2. Secondary Objectives

Secondary objectives of this study are to determine the number of patients in glucocorticoid-free remission and the change in prednisone dose compared to baseline at Week 16, after the open-label period (Period 1) of the study. Additional secondary objectives at both Week 16 and Week 28 are to demonstrate that sarilumab treatment is effective for reducing disease manifestation-specific metrics, for improving laboratory parameters, and for reducing cumulative prednisone dose. An important secondary objective is to demonstrate safety in this patient population.

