## 10. MEASUREMENTS

### 10.1 Primary and Secondary Outcome measures

*Primary endpoint:* The primary endpoint is the flare-free survival of sarilumab-treated patients compared to placebo-treated controls in the double-blind randomized withdrawal period (Period 2) from Week 16 to Week 28. Patients will be considered to have flared if they receive rescue medication including increased glucocorticoids, or if they discontinue the study treatment in order to start a different therapy.

*Secondary endpoints:* The following secondary endpoints will all be assessed at Week 16 and Week 28 compared to baseline as a paired analysis: the change in the extrapulmonary physician organ severity tool (ePOST) score (17 organs rated 0-6, for a total score range of 0-102) [16], the change in global score of sarcoidosis using a visual analogue scale (VAS) by both the patient and physician (distance in mm measured on a 10 cm line), the change in FACIT-F score (fatigue scale ranging from 0-52 with higher score meaning less fatigue), the change in the Health Assessment Questionnaire (HAQ), the change in prednisone dose, the change in serum angiotensin converting enzyme (ACE), serum immunoglobulin G (IgG) levels, serum calcium, urine calcium, and serum 25-hydroxy vitamin D (25-OH-vit D), the change in pulmonary function tests (FVC, FEV1, and DLCO), the change in ALT, AST, and alkaline phosphatase, the change in serum creatinine and urine protein levels, the change in the Sarcoidosis Activity and Severity Index for cutaneous sarcoidosis (7 parameters scored 0-4 for a total score range of 0-28) [17], the change in CK, aldolase, and LDH, and the change in size of sarcoidosis lesions (i.e. enlarged lymph nodes, hepatic nodules, pulmonary nodules) by CT imaging. For patients with known or suspected ocular involvement, the secondary endpoint of change in ophthalmology global assessment of ocular sarcoidosis using a visual analogue scale (VAS) (distance in mm measured on a 10 cm line) [18] will be assessed, as well as the change in any one or more of the following parameters: best corrected visual acuity (BCVA), slit lamp examination (including grading of anterior chamber cells), tonometry, dilated indirect ophthalmoscopy (including grading of vitreous cells and haze), optical coherence tomography (OCT) and OCT angiography, color fundus photography, and fluorescein angiography.

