# **12. STATISTICAL CONSIDERATIONS**

## **12.1 Statistical Design**

Patient characteristics including demographics, medical history, and concomitant medications will be summarized. The summaries will be done using descriptive statistics, eg, mean, standard deviation, median, minimum and maximum for quantitative values and counts and percents for qualitative variables.

The primary efficacy analysis of flare-free survival in Period 2 from Week 16 to Week 28 will use the intention-to-treat (ITT) population and will be assessed with Kaplan-Meier methods. **Patients will be considered to have flared in Period 2 if they receive rescue medication including increased glucocorticoids, or if they discontinue the study treatment in order to start a different immunosuppressive therapy.**

For Period 1, secondary endpoint variables will be treated as continuous and the values at Week 16 will be compared to Baseline values using Wilcoxon signed-rank tests. The number of patients in glucocorticoid-free remission at week 16 will be reported. Patients will be considered non-responders in Period 1 if they are unable to complete the glucocorticoid taper, receive rescue medication including increased glucocorticoids, or discontinue the study treatment in order to start a different therapy. For Period 1 secondary efficacy endpoints, non-responders will be included in the analysis only if their prednisone dose is equal to or less than the starting dose and stable for the 4 weeks preceding Week 16. The rationale for this is that patients who flare despite sarilumab therapy might be given high doses of steroids, thus improving their endpoints and falsely attributing the success to sarilumab. As a sensitivity analysis, we will also assess the secondary outcomes using the baseline observation carried forward (BOCF) for those patients deemed non-responders.

For Period 2, time to first flare will be compared using a 2-sided log-rank test. The proportion of patients in glucocorticoid-free remission at week 28 in sarilumab-treated patients compared to placebo controls will be analyzed using a Fisher's exact test. The remaining secondary endpoint variables will be treated as continuous and the values at Week 28 will be compared to Week 16 and to Baseline values using Wilcoxon signed-rank tests. We will not perform any corrections for multiple hypothesis testing due to the exploratory nature of this pilot study which solely aims to generate areas of potential future investigation.

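### Signed-rank test of Week 16 prednisone dose against Baseline does not test a sarilumab effect: a mandatory taper and the inclusion rule leave only zero or negative changes

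*Combined protocol and SAP*

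**What the plan says.** - **Objective.** Section 1.2 sets out to determine "the change in prednisone dose compared to baseline at Week 16, after the open-label period (Period 1) of the study", alongside a count of patients in glucocorticoid-free remission. A separate sentence there aims to demonstrate, at Weeks 16 and 28, that sarilumab is effective "for reducing cumulative prednisone dose".
- **Endpoint.** Section 10.1 lists "the change in prednisone dose" among the secondary endpoints that "will all be assessed at Week 16 and Week 28 compared to baseline as a paired analysis". Cumulative prednisone is not on that list.
- **Test.** For Period 1, Section 12.1 states that "the values at Week 16 will be compared to Baseline values using Wilcoxon signed-rank tests". For Period 2 it compares Week 28 with both Week 16 and Baseline by the same test.
- **Taper.** The Synopsis (Treatment Summary) states: "Starting at week 4, all patients will begin a scheduled prednisone taper that will take place from week 4 until week 16". It adds: "Patients will be required to adhere to this tapering protocol". Entry doses between 40 and 60 mg are to be "reduced to 40 mg daily by the end of week 3 at the clinician's discretion".
- **Design.** Section 2.4 describes Period 1 as single-arm and open-label.
- **Who is analysed.** Under Section 12.1, Period 1 non-responders are patients who cannot complete the taper, receive rescue, or stop study treatment to start another therapy. They enter the Period 1 secondary analyses only if their prednisone is at or below the starting dose and was stable over the four weeks before Week 16. A sensitivity analysis carries the baseline value forward (BOCF) for non-responders.
- **Reported alongside.** Section 12.1 also reports how many patients are in remission at Week 16, with no interval specified.

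**The concern.** A signed-rank test against zero asks whether dose changes are symmetric about no change. Here the protocol itself orders the change, no untreated group shows what the taper alone would achieve, and no reference reduction is given. The inclusion rule then removes patients whose dose ended above where it began, which are the observations that could pull the result the other way.

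The authors' reason for the rule is sound for the other endpoints: high rescue doses could improve them and the gain be credited to sarilumab. For prednisone dose itself, the rule selects on the outcome.

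At stake is interpretation. A small p-value for prednisone reduction would be easy to present as steroid-sparing efficacy, although it can arise when few patients, or none, reach the state that the trial is about.

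**Working it through.** **Inputs.** 15 patients in Period 1 and an assumed 80% response (Section 12.3); the test, inclusion rule and BOCF analysis (Section 12.1); the taper (Synopsis). Section 12.1 gives no alpha for this test, so two-sided 0.05 is assumed. I take the starting dose in the inclusion rule to be the Baseline dose. The taper steps are not in the available text, and the results below do not depend on them.

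**Plan's own figure.** The plan states no power or effect size for this test, so there is none to reproduce. Its only Period 1 arithmetic is 15 × 0.80 = 12 responders, which is correct.

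**Step 1: possible signs.** Responders have completed the taper, so their change is negative. Included non-responders are at or below the starting dose, so theirs is zero or negative.

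**Step 2: p-value.** The standard signed-rank test drops zeros. If all n non-zero changes have the same sign, the exact two-sided p = 2/2^n:

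| Included patients below baseline (n) | p |
|---|---|
| 5 | 2/32 = 0.0625 |
| 6 | 2/64 = 0.031 |
| 8 | 2/256 = 0.0078 |
| 11 | 2/2,048 = 0.00098 |
| 12 | 2/4,096 = 0.00049 |
| 15 | 2/32,768 = 0.00006 |

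The p-value depends only on how many included patients are below baseline. It does not depend on the size of the cut or on remission. If all 15 cuts are equal, the normal approximation gives 0.00011, with the same conclusion.

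**Step 3: no remission.** Suppose all 15 fail the taper but are held below baseline with four weeks of stable dosing. Remission is 0/15 and p = 0.00006. Under BOCF all 15 changes are zero and there is no test result.

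**Step 4: a less extreme case.** Suppose 6 of 15 respond, half the planned 12, and the other 9 contribute zero, either because they are back at the starting dose or through BOCF. Then p = 0.031 in the main and the BOCF analysis alike. The exact 95% CI for 6/15 is 16% to 68%.

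**Step 5: how often.** If every non-responder contributes zero, p < 0.05 needs at least 6 responders. The binomial probability of 6 or more out of 15 is 99.99% at a true response of 80%, 97% at 60% and 60% at 40%.

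**Step 6: effect of the inclusion rule.** Suppose instead that all 15 were analysed, with 2 above baseline and 13 below. Then p would run from 0.0003 (increases the smallest changes) to 0.083 (increases the largest). With 3 above baseline the range is 0.0009 to 0.33. The rule excludes these patients.

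**The case against.** The case for leaving the plan alone has substance.

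- **The informative result is already planned.** The Week 16 remission count is named in both Section 1.2 and Section 12.1. This stands. What is missing is an interval, while the less informative quantity gets the formal test.
- **BOCF would expose the worst case.** This stands for 0 of 15. It does not help at 6 of 15, where BOCF gives the same 0.031, and it remains a sensitivity analysis.
- **The worst case is demanding.** All 15 would have to fail, settle below baseline and be stable from about Week 12, while the taper runs to Week 16. It is permitted but extreme.
- **The study is exploratory.** Section 12.1 uses this to justify no multiplicity correction. It does not make a comparison with zero informative when the protocol orders the change.

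A reader might go further and infer that significance is assured whatever sarilumab does. The documents do not support that. Patients are glucocorticoid-dependent at entry, Section 12.1 expects that those who flare may receive high steroid doses, and a patient back at the starting dose contributes zero; with 5 patients below baseline p is 0.0625. The early step down to 40 mg applies only to higher entry doses and is at the clinician's discretion.

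A reader might also infer that Section 1.2 sets out to demonstrate that sarilumab lowers the prednisone dose. For dose change the verb is to determine. The demonstration wording attaches to cumulative prednisone, for which Section 10.1 lists no endpoint and Section 12.1 names no test.

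**Conclusion.** The point holds in a limited form. In Period 1 the included changes in prednisone dose are zero or negative by design, so rejecting the zero-change null is not evidence of a sarilumab effect. Six included patients below baseline are enough for p = 0.031, and p can reach 0.00006 with no remissions in the extreme case. This rests on a two-sided 0.05 level, on the starting dose meaning the Baseline dose, and on zeros being dropped.

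The Week 28 comparison with Baseline shares the problem, because the same taper lies behind it. The inclusion rule is written for Period 1 only, so the one-sign argument does not carry over in full.

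The matter concerns a secondary, exploratory analysis. The placebo-controlled Period 2 primary comparison is untouched. The change is worth making because it is cheap and prevents a misleading efficacy reading.

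**What to change.** - **Section 12.1, dose.** Drop the signed-rank test against Baseline for prednisone dose at Week 16 and at Week 28. Describe dose for all enrolled patients: individual values, median and range.
- **Section 12.1, remission.** Report the planned Week 16 remission count using the plan's own responder definition, with all 15 enrolled patients as denominator and an exact 95% CI. A bare count of patients at 0 mg would not do, since it could include someone who switched therapy or broke the tapering schedule, whom the plan classes as a non-responder. The 80% may be shown as the planning assumption, not as an efficacy benchmark.
- **Section 1.2.** State that no claim that sarilumab reduces cumulative prednisone is drawn from the uncontrolled Period 1.

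The cost is a few lines of text. The daily steroid diary already supplies the data, and treatment and taper are unchanged. The downside is the loss of a favourable-looking exploratory p-value.

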## 2. BACKGROUND

### 2.1 Sarcoidosis

Sarcoidosis is a rare disease, but one that carries a high risk of morbidity and mortality with a 5 and 10-year mortality rate of 4 and 9% [1]. The prevalence is estimated at 10-20 per 100,000 of the general population, with roughly 50,000 people affected in the United States [2]. The incidence varies by region and ethnicity; the disease is roughly four times more common in blacks.

Sarcoidosis typically presents between the ages of 20 and 60 and a higher mortality exists in patients older than 55, non-Hispanic African Americans, and women [1]. The lungs are affected in the vast majority of patients (~90%), leading to fatigue, dyspnea, and often pulmonary fibrosis which can result in death. When the liver is affected, it can cause hepatic failure requiring transplantation. Ocular inflammation can permanently damage the eye, skin rashes are disfiguring, enlarged lymph nodes and glands can be painful, and inflammatory arthritis can be debilitating.

Sarcoidosis is often chronic, requiring long-term immunosuppression. There are no established guidelines for the treatment of sarcoidosis, but the mainstay therapy is glucocorticoids. It is well established that prolonged use of glucocorticoids has a number of harmful effects, including glucose intolerance, osteoporosis, weight gain, hypertension, hyperlipidemia, infection, insomnia, cataracts, gastrointestinal perforation, and mood changes [3-5]. Thus, it is essential for patients who do not respond to glucocorticoids to be treated with additional agents in hopes of minimizing exposure to steroids. Typically, a disease modifying anti-rheumatic drug (DMARD), such as methotrexate or azathioprine, is added to prednisone. When this fails, and for severe manifestations, more potent drugs are used such as cyclophosphamide or a biologic drug such as a TNF-inhibitor. Despite these therapies, many patients have ongoing sarcoidosis symptoms and organ injury.

### 2.2 Sarilumab

Sarilumab is a recombinant human monoclonal antibody of the immunoglobulin G1 (IgG1) kappa isotype directed against the interleukin-6 receptor  $\alpha$ -subunit (IL-6Ra). Sarilumab binds to human

IL-6R $\alpha$  and has been demonstrated to block interleukin-6 (IL-6) mediated signaling. Sarilumab, formulated for subcutaneous (SC) injection at doses of 150 and 200 mg every 2 weeks (q2w), was approved for the treatment of RA in Canada on 12 January 2017, the United States (US) on 22 May 2017, European Union (EU), Norway, Iceland, and Liechtenstein on 23 June 2017, and Japan on 27 September 2017. Sarilumab is also in Phase 2 development for the treatment of polyarticular-course juvenile idiopathic arthritis (pcJIA) in pediatric patients.

As of 12 January 2018, the global sarilumab RA clinical development program consisted of 10 Phase 1 clinical pharmacology studies and 9 Phase 2/3 studies.

*Phase 1 studies:*

Of the 10 Phase 1 clinical pharmacology studies, 8 studies were conducted in patients with RA receiving methotrexate (MTX) and 1 study was conducted in healthy subjects. All but 2 of these studies (TDR10805/6R88-RA-0802 and INT12684) were single dose studies.

*Phase 2/3 studies in RA:*

Of the 9 Phase 2 and 3 studies of the global RA program, 5 studies have been completed (EFC11072/SARIL-RA-MOBILITY, EFC10832/SARIL-RA-TARGET, SFY13370/SARIL-RA-ASCERTAIN, EFC13752/SARIL-RA-ONE, MSC12665/SARIL-RA-EASY); 2 were prematurely terminated (ACT11575 and EFC11574/SARIL-RA-COMPARE) due to the operational feasibility and lack of ability to provide a timely result versus the plan but not due to any safety issue; and 2 studies are ongoing: the open-label extension part of EFC14092/SARIL-RA-MONARCH (double-blind part of this study has been completed) and the uncontrolled extension Phase 3 study LTS11210 (SARIL-RA-EXTEND) that enrolled patients from studies EFC11072, EFC10832, EFC13752, SFY13370, and ACT11575.

The global RA program has enrolled patients with RA from over 40 countries worldwide, who required alternatives to oral disease-modifying anti-rheumatic drugs (DMARDs) or tumor necrosis factor alpha (TNF- $\alpha$ ) antagonists because of inadequate control of disease activity or intolerance to these agents. This program entered Phase 2/3 with an operationally seamless study, EFC11072, consisting of a combined dose-ranging (Phase 2) part and a confirmatory (Phase 3) part, which was conducted in patients with active RA who were inadequate responders to MTX therapy.

In the dose-ranging part of the study (EFC11072/Part A), 5 dose regimens (100 mg q2w, 150 mg q2w, 200 mg q2w, 100 mg every week [qw], and 150 mg qw) and placebo were tested in 306 randomized patients. The demographic and disease characteristics at baseline were similar across all treatment groups.

Based on an in-depth analysis of the Phase 2 study results, the 150 mg q2w and 200 mg q2w doses were selected for evaluation in 2 pivotal Phase 3 trials in RA (EFC11072 Part B and EFC10832) where sarilumab was tested as a combination therapy with a conventional DMARD.

In the Phase 3 confirmatory part of EFC11072 (Part B), both sarilumab dose groups showed clinically relevant and statistically significant ( $p<0.0001$ ) improvements compared with placebo in all 3 co-primary endpoints: improvement in signs and symptoms of RA at 24 weeks (as defined by 20% improvement on American College of Rheumatology [ACR] definition of improvement

criteria [ACR20]), improvement in physical function (as assessed by Health Assessment Questionnaire Disability Index [HAQ-DI]) at Week 16 and inhibition of progression of structural damage at Week 52. Study EFC11072 Part B, Cohort 2 (where patients were randomized to either placebo or one of 2 selected doses: 150 mg q2w or 200 mg q2w) demonstrated that sarilumab 200 mg q2w and 150 mg q2w inhibited the 1-year rate of radiographic progression by 91% and 68% relative to placebo, respectively.

In addition to study EFC11072, efficacy of sarilumab was demonstrated in study EFC10832, conducted in patients who had an inadequate response or intolerance to one or more TNF- $\alpha$  antagonists. For the primary endpoints of ACR20 at Week 24 and HAQ-DI at Week 12, significant improvement was observed in patients treated with sarilumab 200 mg q2w and 150 mg q2w compared with placebo, showing that patients who previously had an inadequate response or intolerance to TNF- $\alpha$  antagonists responded to treatment with sarilumab.

Although demonstration of efficacy was not the primary objective for the other Phase 3 clinical trials in RA where sarilumab was administered either as monotherapy (EFC13752, EFC14092) or with concomitant DMARD therapy (SFY13370 and MSC12665), clinical efficacy profiles in these studies were consistent with results from the active-controlled Phase 3 studies in the global program (EFC11072 Part B, and EFC10832).

Patients who completed studies EFC11072, EFC10832, EFC13752, and SFY13370 had the option to enroll in the ongoing long-term extension study LTS11210 at the highest tested dose (200 mg q2w). In this study, the efficacy of sarilumab administered concomitantly with DMARDs was sustained for the duration of the available follow-up period: approximately 3.8 years and 2.1 years for patients initially randomized in EFC11072 Part B and EFC10832, respectively. The persistence of efficacy was consistent across all the domains of treatment of RA, namely signs and symptoms, structural damage, and physical function.

